activity in cocaine users in a sham-controlled trial evaluating the effects of a single cTBS session.(9,10) Prior work showed that rTMS to the DLPFC reduced MPFC activity in controls but not cocaine users. The findings of studies by Hanlon and colleagues supported a National Institute on Drug Abuse-funded randomized sham-controlled trial of MPFC cTBS for cocaine use disorder.(9)

Study Sites

The University of Iowa, the University of Utah, and the University of New Mexico are participating in this study.

Subject Recruitment

Subjects will be recruited through advertising as well as through colleague referral and medical record review. Patients admitted to a crisis stabilization unit, inpatient unit, or partial hospitalization or intensive outpatient substance use disorder treatment program, or seen in an outpatient addiction medicine clinic, with a diagnosis of methamphetamine use disorder will be provided with information about the study by clinicians to consider participation. Initial discussions will take place in private rooms. Posters and brochures will also be located in care locations.

Inclusion/Exclusion Criteria

Inclusion criteria:

- Diagnosed with an active methamphetamine use disorder
- Is engaged in psychosocial treatment or articulates a plan to engage in psychosocial treatment for methamphetamine use disorder during the study period
- Age 18 to 60 years
- Able to consent for treatment and research participation
- English-speaking

Exclusion Criteria:

- Age less than 18 years

- Patients that are excluded during TMS assessment including: patients with epilepsy or seizure disorder, patients with implanted ferromagnetic equipment in their face or skull near the stimulation target.
- Current medical treatment with clozapine or stimulants.
- Current diagnosis of bipolar disorder, schizoaffective disorder, schizophrenia, that is deemed by research team psychiatrists not to have been drug-induced. Psychotic disorder not associated with drug use per the MINI International Neuropsychiatric Interview. Psychosis NOS, in remission, or drug-induced psychotic episodes are not exclusion criteria since these may be related to methamphetamine misuse.
- Lacks the mental capacity to provide informed consent (i.e. not able to demonstrate understanding of the risks and benefits of participation)
- Has a court appointed guardian.
- Status as a prisoner.
- Receiving treatment as an alternative to incarceration.
- Unstable medical illness.

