Screening questions that warrant follow up if the participant answers "yes":

- Have you been diagnosed with a methamphetamine use disorder? (follow up- providers to determine if participant should have a methamphetamine use diagnosis, if not currently diagnosed)
- Are you claustrophobic or afraid of small, closed-in spaces? (follow-up- participant needs to confirm that they can handle being in an MRI machine through additional questions)
- Do you have a problem with loud noises? (follow-up- participant needs to confirm that the noises from the MRI are not too loud through additional questions)
- Have you ever had a neurosurgical procedure? (follow up- type of procedure matters)
- Have you been diagnosed with another neurological disorder? (follow-up- type of disorder matters)
- Are you able to make it to all visits for this study without assistance?
Additional information: This involves a baseline visit, then visits five days a week for two weeks and three days a week for two more weeks. The visits need to take place Monday through Friday, but we can start most any day depending on what's convenient for you. There will also be follow-up visits that can be completed by phone or in person one month and two months after the other visits are completed.
 - If not, Please explain any additional services you may need to get to and from study appointments, (i.e. transportation)

Randomization

The randomization scheme was block randomization stratified by study site, with block sizes of 4 and a 1:1 ratio, designed to ensure approximate balance in the number of subjects. Subjects are randomized to receive stimulation at the DLPFC or MPFC first, although both groups receive stimulation at both sites at each visit. The subject is assigned to a group at the first TMS treatment visit.

Intervention

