The study intervention is open-label dual-target theta burst stimulation delivered in sequential fashion to the DLPFC and the MPFC. The order of treatments is determined by the randomization scheme, but the treatments are otherwise identical. Treatment targeting will occur at the Beam F3 and FP1 scalp regions as defined by the 10-20 EEG system. A Magventure MagPro X100 figure-8 coil with theta burst capabilities will be used to deliver the stimulus, including intermittent theta burst stimulation to the DLPFC (2 seconds of 50-Hz triplets delivered at 5 Hz, 8 seconds intertrain interval, 600 total pulses) and continuous theta burst to the MPFC (continuous 50-Hz stimulation triplets, 600 pulses). Stimulation will be delivered at 110% of the resting motor threshold, as determined by the stimulation threshold at which single-pulse TMS stimulation over the motor cortex hand knob region can elicit visible finger movement on 3 of 5 trials, with stimulation dose adjustment for distance from target to coil as needed. Treatment sessions will consist of a single treatment protocol at each stimulation site. Sessions will occur 5 times per week for the first 2 weeks, followed by 3 sessions per week for an additional 2 weeks (16 treatment sessions total).

Study Procedures

This study lasts for a total of 12-13 weeks, and involves 19 visits. Although visits vary from 15 minutes to 5 hours, they average 45-50 minutes. The first week involves a baseline visit that will take 3-4 hours. If the subject elects to participate in the optional EEG and timing task, this will add about an hour to their first visit. Subjects will receive 4 weeks of TMS treatments, and each treatment should take about 15 minutes. The first two weeks of treatment involve 5 visits per week

where the subject receives TMS. The third and fourth weeks of treatment involve 3 visits per week where the subject receives TMS. Additional assessments are done on the last treatment day of each treatment week. These visits, including treatment time, will take about 30 minutes after the first and third weeks of treatment, 45-60 minutes after the second week of treatment, and 3-4 hours after the fourth week of treatment. If the subject elects to participate in the optional EEG and timing task, this will add about an hour to their visit after the fourth week of treatment. Follow-up phone calls lasting 45-60 minutes will take place 4 weeks and 8 weeks after the end of TMS treatment (week 9 and week 13 of the study).

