Assessment visit 1 will take place prior to TMS treatment. Information will be collected on demographics and a history of substance use and medical conditions. Subjects will be screened using the MINI International Neuropsychiatric Interview to ensure they do not have mental health conditions that should lead to exclusion. This may be conducted remotely by a psychiatrist investigator using a HIPAA compliant Zoom meeting if a psychiatrist is not available to perform the MINI on-site. The subject will complete all assessment surveys. They will also complete several psychological tests, including a Flanker task administered with an iPad, and a digitally administered delay discounting task. They will also submit a urine drug screen if there is not a recent result on file in their EHR, or one is not known to be planned for that day. Then they will complete fMRI imaging. This visit should take 3-4 hours. If the subject elects to participate in the optional EEG and timing task, this will add about an hour to this visit. If they elect to participate in this optional EEG and task, investigators will adhere electroencephalogram (EEG) leads to their scalp and then have them perform 2 blocks of the interval timing task where they estimate the passage of a specified (3 or 12 second) passage of time (~22min - 11 min blocks). The beginning of the trial is indicated by the presentation of either a 3 or a 12 on the computer screen which also indicates the duration of time the subject should estimate. During performance, we will collect electroencephalographic data from patients which will be analyzed offline. Within a week of this visit, the subject will begin TMS treatment. TMS treatment could start as early as the same day if the subject prefers and the schedule allows.

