Transcranial magnetic stimulation is a non-invasive method of brain stimulation that relies on electromagnetic induction using an insulated coil placed over the left prefrontal cortex. The coil generates brief magnetic pulses, which pass easily and painlessly through the skull and into the brain. The pulses generated are of the same type and strength as those generated by magnetic resonance imaging (MRI) machines. When these pulses are administered in rapid succession, it is referred to as "repetitive TMS" or "rTMS", which can produce longer lasting changes in brain activity. During the treatment, the patient may experience light-headedness, tapping, tingling, itching, headaches, or muscle twitching while the magnetic coil is turned on. However, TMS has been proven safe in major depressive disorder and the treatment team will be using an FDA-approved protocol for DLPFC iTBS. We will also be using a cTBS protocol that has been previously studied by Hanlon et al, who did not note meaningful differences in adverse effects. Because the TMS device produces a loud click with each pulse, the subject will wear earplugs during treatment to minimize discomfort. The most serious known risk of TMS is the production of a seizure. To minimize this risk, all

subjects with a history of epilepsy or epileptogenic intracranial lesions will be excluded from the study; any subjects that are deemed inappropriate for TMS treatment by the physician who administers TMS will also be excluded from the study.

MRI Risks

A metal object flying through the air toward the magnet and hitting the subject comprises the greatest risk associated with MRI.

- There is a minimal risk to the subject's hearing.
- There is a risk that we will discover an abnormality or disease in the subject, which would otherwise not be found. This risk can increase the psychologically-induced stress associated with participating in this study.
- Although there are no known risks associated with limited exposure to magnetic fields, we cannot rule out the possibility that in the future some risks may be discovered.

Emotional Risks

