This is a pilot study without an untreated control group so will not be able to establish that the treatment is causal in improving outcomes. The overarching goal is to evaluate the ability to recruit and retain subjects, establish safety of the intervention in this population, evaluate target engagement of TMS using fMRI, and to determine the extent to which patient symptoms and substance use appear to improve during participation in treatment. We anticipate approximately 20 subjects, which should be adequate to statistically detect clinically meaningful changes in symptoms and other outcome measures, depending on attrition. We will randomize order of treatments to gather preliminary data on any differences, but do not anticipate power to detect significant differences in effect by order of treatment with this sample size.

Outcomes

Primary outcomes:

1. Retention in the Study: Measured from Baseline to 12 weeks
2. Retention in Psychosocial Treatment: Measured from Baseline to 18 days (self-reported)

Secondary outcomes (used all available data points as specified in figure 2):

1. Functional Connectivity of the Dorsolateral Prefrontal Cortex and Anterior Insula—change from baseline to 4 weeks. Measured by correlation of region activity over MRI time series data, averaged for left and right hemisphere.
2. Functional Connectivity Dorsolateral Prefrontal Cortex and Anterior Cingulate Cortex—change from baseline to 4 weeks. Measured by correlation of region activity over MRI time series data, averaged for left and right hemisphere.
3. Functional Connectivity of the Medial Prefrontal Cortex and Ventral Striatum—change from baseline to 4 weeks. Measured by correlation of region activity over MRI time series data, averaged for left and right hemisphere.
4. Kirby Delay Discounting Questionnaire, 27 Item

5. Number of Days of Methamphetamine Use in the Past Week
6. Urine Drug Screen Positive for Stimulant
7. Brief Substance Craving Scale
8. Brief Addiction Monitor—Use Subscale
9. Brief Addiction Monitor—Risk Factors Subscale
10. Brief Addiction Monitor—Protective Factors Subscale
11. Brief Addiction Monitor—Satisfaction with Progress Toward Achieving Recovery Goals (question 17)
12. Quality of Life Enjoyment and Satisfaction Questionnaire—Short Form
13. Patient Health Questionnaire--8 Item Scale
14. Generalized Anxiety Disorder 7-item Scale
15. Assessment of Recovery Capital
16. Positive and Negative Affect Scale—Positive Affect Score

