17. Positive and Negative Affect Scale—Negative Affect Score
18. Pittsburgh Sleep Quality Index
19. Difficulties in Emotion Regulation Scale--Short Form
20. UPPS-P Impulsive Behavior Scale, 59-item Revised Version

Safety outcomes

Adverse events are reported at each TMS treatment visit, or if otherwise volunteered by subject.

Populations to be analyzed

Intention to treat: Subjects will be analyzed in the groups they were randomized to. However, only complete data will be used, and subjects were discontinued from the study if they missed more than 4 TMS treatments.

Analyses

Descriptive statistics will be examined for demographic and other variables, overall and by intervention group.

For other analyses, a fixed time will be assigned for each study visit, which approximates the time at which the visit would have occurred on a typical study schedule.

Primary outcomes

The primary analysis will compare intervention groups (DLPFC first or MPFC first) on time to discontinuation in the study and time to discontinuation of psychosocial treatment. The latter is defined as a participant indicating they are no longer in or seeking treatment. All subjects were in treatment or planning treatment at baseline, as an inclusion criterion. Time retained in the study or treatment will be described using Kaplan-Meier curves, and intervention groups will be compared using log-rank tests.

Secondary outcomes

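### Fixed blocks of 4 within site, in an open-label trial with no concealment described, leave about 23-33% of assignments knowable in advance; the order comparison is exposed to selection, with probably small impact

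*Combined protocol and SAP*

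**What the plan says.** The Randomization section of the protocol reads: "The randomization scheme was block randomization stratified by study site, with block sizes of 4 and a 1:1 ratio". It adds: "The subject is assigned to a group at the first TMS treatment visit". The Intervention section says: "The study intervention is open-label dual-target theta burst stimulation delivered in sequential fashion to the DLPFC and the MPFC". Order of stimulation is the only planned difference between the groups.

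Two discretionary steps come before assignment:

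- Under TMS Risks: "any subjects that are deemed inappropriate for TMS treatment by the physician who administers TMS will also be excluded from the study".
- Under Study Procedures, after the baseline assessment visit: "Within a week of this visit, the subject will begin TMS treatment". A same-day start is also allowed.

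In the SAP, under Primary outcomes: "The primary analysis will compare intervention groups (DLPFC first or MPFC first) on time to discontinuation in the study". The Secondary outcomes section likewise tests differences between the order groups through group-by-time terms.

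The document does not say who generated or held the list, how an assignment reached the site, or whether site staff were kept unaware of the block size.

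**The concern.** With one known block size, a 1:1 ratio and a separate sequence at each site, anyone who has seen the site's previous assignments can sometimes work out the next one. Open-label delivery means that those who give the treatment do see them. Assigning at the first TMS visit does not help for a slot whose content is already determined, because that content can be known before the visit.

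If the decision on who starts, or who starts next, could depend on a known assignment, the two order groups might differ at entry. A difference in retention or symptoms by order could then reflect selection. Order is the only randomised contrast in the trial, and about 20 subjects are too few to detect or adjust for such a difference.

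**Working it through.** **Inputs.** Block size 4, 1:1, within site (Randomization). Three sites (Study Sites: "The University of Iowa, the University of Utah, and the University of New Mexico are participating in this study"). Total from Sample Size Justification: "We anticipate approximately 20 subjects". That total is given without alpha, power or effect size, so it cannot be reproduced; it serves here only as the number to divide over sites. The plan gives no predictability figure and no site split. The splits below are assumptions.

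**One complete block.** The six orderings of two DLPFC-first and two MPFC-first are equally likely. An assignment is certain when one arm is used up. The best guess is the arm with more slots left.

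| Position | P(certain) | P(best guess correct) |
|---|---|---|
| 1 | 0 | 1/2 |
| 2 | 0 | 2/3 |
| 3 | 1/3 (first two match) | 1/3 × 1 + 2/3 × 1/2 = 2/3 |
| 4 | 1 | 1 |
| Sum | 4/3 (33.3% of 4) | 17/6 (70.8% of 4) |

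Simple randomisation would give 0% certain and 50% guessed.

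**Twenty subjects over three sites.** Each complete block adds 4/3 certain assignments. A last block stopped at three subjects adds 1/3, and one stopped at one or two adds none.

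- 7/7/6: 5/3 + 5/3 + 4/3 = 4.67 (23.3%); best guess 13.33 of 20 (66.7%).
- 10/5/5: 8/3 + 4/3 + 4/3 = 5.33 (26.7%); best guess 13.50 of 20 (67.5%).
- 12/4/4: 12/3 + 4/3 + 4/3 = 6.67 (33.3%); best guess 14.17 of 20 (70.8%).

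Over every split of 20 in which all three sites enrol, the range is 4.67 to 6.67.

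**Randomly varying blocks.** The observer is assumed to know the set of possible sizes (equally likely) but not the size of the current block. Exact enumeration gives:

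| Split | Certain of 20: fixed 4 | 4 or 6 | 4, 6 or 8 | Best guess: fixed 4 | 4 or 6 | 4, 6 or 8 |
|---|---|---|---|---|---|---|
| 7/7/6 | 4.67 | 1.35 | 0.34 | 66.7% | 66.2% | 64.4% |
| 10/5/5 | 5.33 | 1.10 | 0.26 | 67.5% | 66.1% | 64.1% |
| 12/4/4 | 6.67 | 0.85 | 0.29 | 70.8% | 66.9% | 64.9% |

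**Balance.** With fixed blocks of 4, the variance of the difference in group sizes is 1 for a site whose last block stops at one or three subjects, 4/3 if it stops at two, and 0 if it is complete. For 7/7/6 and for 10/5/5 the total is 1 + 1 + 4/3 = 3.33, an SD of 1.8. For 12/4/4 it is 0. Blocks of 4 or 6 give an SD of 1.6 to 1.8 over these three splits; blocks of 4, 6 or 8 give 1.9 to 2.0.

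**Size of a possible bias (illustration only).** Assume 7/7/6, a normal outcome with SD 1, a t-test at 5%, and subjects whose means shift by ±0.25 or ±0.5 SD according to the best guess. If every guess that is not a tie is acted on, fixed blocks of 4 give a spurious order difference of 0.18 or 0.35 SD and rejection in 6.4% or 10.1% of 6,000 replicates. Blocks of 4, 6 or 8 give 0.15 or 0.30 SD and 6.1% or 8.7%. The standard error of the gap between 6.4% and 6.1% is about √(2 × 0.0625 × 0.9375 / 6000) = 0.44 points, so that gap is within simulation noise. If only a quarter of guesses are acted on, fixed blocks give 0.05 to 0.09 SD and 5.0-5.2% rejection.

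**The case against.** The strongest reply is that opportunity has been shown without knowledge or motive.

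- **Knowledge.** The document is dated May 2023 and describes the scheme in the past tense, so it does not show that site staff had the block size in front of them while enrolling. A reader might infer that the list was open to the sites. Silence on concealment does not establish that. What stands is that no safeguard is described.
- **Motive.** Both groups receive both stimulations at every visit, and the document offers no reason to prefer one order for a given subject. This stands, and it is the main reason to expect a small effect.
- **Levers.** Start-day flexibility is described as suiting the subject. Delay changes an assignment only if someone else at the same site is randomised in between, and no accrual rate is given. Nor is it shown that those who judge eligibility follow the sequence. This narrows the route but does not close it.
- **Stakes.** The primary objective is feasibility, and the SAP anticipates no power for order effects. Overall retention and pooled change do not rest on allocation. That is correct, but low power does not protect against bias, and the SAP still labels the order comparison primary.
- **Remedy.** Varying the blocks hardly lowers best-guess accuracy, and the simulated gain is small. That stands too, which is why concealed release belongs in the change alongside varying blocks.

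**Conclusion.** The point holds as one of exposure. Fixed blocks of 4 within site, open-label delivery and no described concealment would let staff who know the size and track their site's assignments foresee 23-33% of them. That figure rests on 20 subjects, all three sites enrolling, and an assumed split.

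A reader might go further and infer that the groups were selected, or that an order difference would be materially biased. The document supports neither: it contains no sign that anyone acted on a predicted assignment, and the larger simulated biases require every usable guess to be acted on. The likely impact is small and confined to the between-order comparisons. The change is still worth making, because it is cheap and protects the trial's only randomised contrast.

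**What to change.** **If subjects remain to be randomised**, replace the sentence with text such as:

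> Randomisation is 1:1, stratified by site, in permuted blocks of randomly varying size. The list is generated by a statistician who has no contact with participants. Block sizes are held in a document not available to site staff. Each assignment is released only after final eligibility, including the TMS physician's assessment, has been recorded and the participant has arrived for the first TMS visit.

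The sizes should not appear in the protocol. Sizes 4 and 6 would serve, with about 0.9 to 1.4 certain assignments of 20. Sizes 4, 6 and 8 go lower, to about 0.3 in the splits tabulated.

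**Cost.** A new allocation list and a means of controlled release. The document describes REDCap for data storage only, so its use for allocation would need to be confirmed. Chance imbalance is similar to now with 4 and 6 and slightly larger with 4, 6 and 8; the exception is a split in which every block of 4 would be complete, where the present scheme balances exactly. Imbalance costs little precision: 12:8 in place of 10:10 raises the variance of a group difference by (1/12 + 1/8) / (1/10 + 1/10) = 1.04, or 4%.

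**If enrolment is complete**, report that fixed blocks of 4 were used open-label, state what concealment was in place, and treat any order difference as exploratory and open to selection. This costs a few sentences.

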Most secondary outcomes will be examined using linear mixed models. These allow for estimation of within group change over time as well as between group differences in change over time. Group by continuous time interaction terms will be the primary test of hypotheses for differences between groups. For outcomes measured at only two time points (baseline and week 4), if sample size is not adequate or mixed models do not converge, changes from baseline to the second measure will be calculated. Wilcoxon-rank sum tests or t-tests comparing differences in changes from baseline to week 4 will be used to compare groups, as appropriate based on the data distribution. A generalized estimating equations model clustered on subject with a logit link, with empirical standard error estimates, will be used to analyze the outcome of positive urine drug screens for stimulants, as this is binary, and this approach does not assume a correlation structure. The primary analysis of this outcome will still use a group by continuous time interaction to examine whether the odds of a positive urine drug screen decreases over time in each group, and whether any reduction over time differs between groups.

Missing data

As this is a pilot study with a small sample size, and dropout is expected, analyses will use all available data as feasible for randomized subjects who received at least one treatment, irrespective of the number of data points collected. For changes in functional connectivity as measured by MRI, only subjects with both baseline and 4-week assessments will be included. No imputation of data will be performed.

References

1. Governor's Office of Drug Control Policy. News Release - Iowa Drug Control Report: Life-Changing Progress Amid Evolving Threats.
<https://odcp.iowa.gov/news-release-iowa-drug-control-report-life-changing-progress-amid-evolving-threats>. Published 2019. Updated November 13, 2019. Accessed December 13, 2019, 2019.
2. Iowa Department of Public Health. Substance Abuse Brief, December 2018, Issue 7.
https://idph.iowa.gov/Portals/1/userfiles/133/IASubAbuseBriefNewsletterDec2018_Final.pdf. Published 2018. Accessed December 13, 2019, 2019.

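### Randomisation is stratified by site, but the log-rank, mixed-model and change-score comparisons of stimulation order leave site out and can be conservative if sites differ

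*Combined protocol and SAP*

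**What the plan says.** The Randomization section of the protocol describes "block randomization stratified by study site", "with block sizes of 4 and a 1:1 ratio". Under Study Sites, "The University of Iowa, the University of Utah, and the University of New Mexico are participating in this study", so there are three strata.

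The SAP makes the comparison of the two orders its primary analysis. For time to leaving the study and time to leaving psychosocial treatment, "intervention groups will be compared using log-rank tests". For most secondary outcomes a linear mixed model is used: "Group by continuous time interaction terms will be the primary test of hypotheses for differences between groups". If the sample is too small or the model fails for an outcome measured only twice, "Wilcoxon-rank sum tests or t-tests comparing differences in changes from baseline to week 4 will be used to compare groups". Urine screens go into a GEE with empirical standard errors.

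None of these analyses names site as a stratum or covariate, and no reason is given. The SAP expects about 20 subjects and says the investigators "do not anticipate power to detect significant differences in effect by order of treatment with this sample size". It states no significance level and plans no confidence intervals.

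**The concern.** Balancing the two orders within site removes site differences from the true sampling variation of the between-order contrast. A test that ignores site still counts those differences as noise. If site predicts the outcome being compared, the estimated standard error is too large, the true level falls below the nominal one, and precision is lost.

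The log-rank tests are the most exposed, because they carry the primary analysis and because retention is not a change score in which site differences could cancel. Site differences in retention are plausible: recruitment spans crisis, inpatient, partial-hospital, intensive-outpatient and clinic settings, and the second primary outcome is remaining in psychosocial treatment. What is at stake is precision in a very small sample, and the risk that a null result from a conservative test is read as evidence that order does not matter.

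**Working it through.** **Inputs from the documents:** three sites, blocks of 4, 1:1, about 20 subjects. **Assumed, because the documents do not give them:** two-sided 5% level, site sizes, dropout by site, and the share of outcome variance due to site. The plan has no figure of its own to reproduce, since it states no effect size, SD, event rate or power.

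**1. Change score, closed form.** Take sites of 8/8/4 (all multiples of 4, so exact balance) and fixed site differences explaining a share ρ of the variance σ² of change.
- True variance of the between-order difference: 4(1−ρ)σ²/n.
- Expected pooled variance used by the t-test: [(1−ρ) + ρ·n/(n−2)]σ².
- At ρ = 0.2, n = 20: 0.8 + 0.2 × 20/18 = 1.022. The SE ratio is √(1.022/0.8) = 1.130.
- Critical values are 2.101 (18 df, unadjusted) and 2.120 (16 df, adjusted). The interval ratio is 1.130 × 2.101/2.120 = 1.12, so the unadjusted interval is 12% wider.
- True level is approximately P(|t₁₈| > 2.101 × 1.130) = 2.9%.
- At ρ = 0.1, the same steps give 5% wider and a level of 3.9%.
- At ρ = 0, the ratio is 2.101/2.120 = 0.99, so adjusting makes the interval about 1% wider.

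If site effects are instead drawn at random, three sites realise only part of the nominal site variance (for 8/8/4, 1 − 0.16 − 0.16 − 0.04 = 0.64 on average), so the effect is smaller. Simulated t-test levels over several site splits were then 4.2-4.7% at a 10% share, 3.5-4.4% at 20% and 2.8-3.6% at 30%. With site in the model the level was 4.5-5.2%.

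**2. Log-rank test, simulation.** 20 subjects, blocks of 4 within site, sites of 7/7/6, 8/8/4 or 12/4/4. Ranges run over site splits and separate simulations. Monte Carlo error is about 0.2-0.35 points.

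| Assumed site difference | Level, unstratified | Level, site-stratified |
|---|---|---|
| None | 4.7-5.1% | 4.7-5.4% |
| Hazard ratios 1/1.5/0.67 | 4.1-4.8% | 4.5-5.2% |
| Hazard ratios 1/2/0.5 | 3.7-4.8% | 5.1-5.5% |
| 12-week dropout 30/50/70% | 3.3-4.4% | 4.4-5.8% |
| 12-week dropout 25/50/85% | 2.1-3.4% | 4.9-6.2% |

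The last two rows imply hazard ratios between the extreme sites of ln 0.30/ln 0.70 = 3.4 and ln 0.15/ln 0.75 = 6.6.

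Power at an order hazard ratio of 3, sites 8/8/4, unstratified v stratified:
- dropout 25/50/85%: 31% v 41%
- site hazard ratios 1/2/0.5: 36% v 40%
- site hazard ratios 1/1.5/0.67: 40% v 40%
- identical sites: 50% v 47%

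**3. Slope test** (standing in for the mixed model, complete data). The level is 5.0% with no site effect and 4.7-4.8% when site explains 30-60% of variance in level only. It is 4.8% when site explains 10% of slope variance and 4.0% at 30%. Only site differences in change matter here.

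**4. Urine-screen GEE** (independence working correlation, empirical SE, 20 clusters). The level is 6.7% with no site effect and 6.7-7.6% with one (Monte Carlo error about 0.65 points). This is above 5%, and it arises without any site difference.

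The Wilcoxon test and the 18-day psychosocial-retention outcome were not simulated.

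**The case against.** A reader might infer that every between-order test runs below 5% and every interval is too wide. The documents do not support that.
- The loss depends on site being prognostic, and no between-site figure is given. With modest site differences the log-rank level is 4.1-4.8% and there is no power to gain.
- The most striking log-rank figures need a 6.6-fold hazard ratio between sites.
- Stable scanner or clinic offsets largely drop out of change scores and slopes.
- The GEE errs in the opposite direction.
- The 5% level and the intervals are conventions supplied here; the SAP states neither.

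The plan also treats the order comparison as preliminary and disclaims power for it. Both groups receive both stimulations at every visit, so an order hazard ratio of 3 is a very large effect to expect. A conservative test creates no false positives, and the Kaplan-Meier descriptions and within-group changes do not rest on the order contrast.

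All of this stands and limits the weight of the point. It does not remove the mismatch: the SAP names the order comparison as its primary analysis, and that analysis ignores the one factor on which the randomisation was balanced. A disclaimer of power is not a reason to give up precision that costs little to keep.

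**Conclusion.** The point holds conditionally. Site is missing from the log-rank, mixed-model and change-score comparisons by order. If sites differ in retention or in change over time, those tests can be conservative. For the log-rank test this means a level of about 3-4% under a 30/50/70% dropout pattern and about 2-3.5% under 25/50/85%. For a change score with site explaining 20% of variance, it means roughly 3-4%. If sites are alike nothing is lost by omitting site. All sizes rest on assumed site sizes, dropout and site effects with 20 subjects. Importance is modest, because feasibility is the main objective and the order comparison is declared exploratory in effect.

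**What to change.** - **Primary outcomes:** make the site-stratified log-rank test the between-order test for both.
- **Two-time-point comparisons:** regress change on order with site as a covariate, or use a site-stratified (van Elteren) rank test in place of the Wilcoxon test, which cannot take a covariate.
- **Mixed models:** add site, and site-by-time where the model supports it. Site-by-time is the term that addresses site differences in slope. State in advance a fallback to the simpler model if the fuller one does not converge.
- **Reporting:** give unadjusted results as sensitivity analyses. Parts of the Randomization and analysis-population text are in the past tense; if outcomes have already been seen, label the site-stratified results post hoc.
- **Alternatively:** state why site is left out with three small strata.

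The small-cluster behaviour of the GEE is a separate matter that adding site would not cure.

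Cost: SAP wording; a few points of log-rank power if sites are identical (50% v 47% in the example above); and 2 degrees of freedom for site, or 2 + 2 = 4 with site-by-time. The larger model adds to the convergence risk that the SAP already foresees, hence the fallback.
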